8. SAFETY AND TOLERABILITY

Appendix A provides a list of data displays. Sample data displays are included in a separate document.

8.1. General Considerations

Summary tables may be replaced with listings when appropriate. For instance, an AE frequency table may be replaced with a listing if it only contains a few unique PTs reported on relatively few participants. Unless otherwise stated, table summaries will be limited to TEAEs.

8.2. Adverse Events

8.2.1. Adverse Event Definitions

A TEAE is any AE either reported for the first time or worsening of a pre-existing event after the first dose of study drug. Analysis of AEs (as discussed below) will be limited to TEAEs, but data listings will include all AEs regardless of their timing in relation to study drug administration. For purposes of analysis, all AEs will be considered TEAEs unless the AE can unequivocally be defined as not treatment-emergent.

Adverse events will be tabulated by MedDRA (v19.0) PT and SOC. Severity of AEs will be graded using the NCI CTCAE v4.03. The CTCAE reporting guidelines and grading details are available on the Cancer Therapy Evaluation Program website.

The subset of TEAEs considered by the investigator to be related to any study drug will be considered to be treatment-related TEAEs. If the investigator does not specify the relationship of the TEAE to study drug, the TEAE will be considered to be treatment-related. The incidence of TEAEs and treatment-related TEAEs will be tabulated. In addition, serious TEAEs will also be tabulated.

8.2.2. Dose-Limiting Toxicities

The participants with DLTs and the type of DLT will be listed by dose level.

8.2.3. Adverse Event Summaries

An overall summary of AEs by treatment group will include the following:

- Number (%) of participants who had any TEAEs
- Number (%) of participants who had any serious TEAEs
- Number (%) of participants who had any Grade 3 or higher TEAEs
- Number (%) of participants who had any TEAEs related to INCB001158
- Number (%) of participants who had any TEAEs related to pembrolizumab
- Number (%) of participants who had any TEAE leading to temporary interruption of INCB001158
- Number (%) of participants who had any TEAE leading to temporary interruption of pembrolizumab

CONFIDENTIAL

- Number (%) of participants who had any TEAE leading to permanent discontinuation of INCB001158
- Number (%) of participants who had any TEAE leading to permanent discontinuation of pembrolizumab
- Number (%) of participants who had any TEAE leading to INCB001158 dose reductions
- Number (%) of participants who had any fatal TEAEs
- Number (%) of participants who had an irAE

An overall summary of irAEs by treatment group will include the following:

- Number (%) of participants who had an irAE
- Number (%) of participants who had any Grade 3 or higher irAEs
- Number (%) of participants who had any irAEs related to INCB001158
- Number (%) of participants who had any irAEs related to pembrolizumab
- Number (%) of participants who had any irAEs leading to discontinuation of INCB001158
- Number (%) of participants who had any irAEs leading to discontinuation of pembrolizumab
- Number (%) of participants who had any irAEs leading to discontinuation of INCB001158 and pembrolizumab
- Number (%) of participants who had any irAEs leading to discontinuation of INCB001158 or pembrolizumab
- Number (%) of participants who had irAEs leading to INCB001158 dose interruption and/or reductions
- Number (%) of participants who had irAEs leading to pembrolizumab dose interruption
- Number (%) of participants who had any fatal irAEs

The following summaries will be produced by MedDRA term (if 10 or fewer participants appear in a table, a listing may be appropriate):

- Summary of TEAEs by MedDRA SOC and PT
- Summary of TEAEs by MedDRA PT in decreasing order of frequency
- Summary of Grade 3 or higher TEAEs by MedDRA SOC and PT
- Summary of Grade 3 or higher TEAEs by MedDRA PT in decreasing order of frequency
- Summary of serious TEAEs by MedDRA PT in decreasing order of frequency

- Summary of pembrolizumab treatment-related TEAEs by PT in decreasing order of frequency
- Summary of INCB001158 treatment-related TEAEs by MedDRA PT in decreasing order of frequency
- Summary of TEAEs with a fatal outcome by MedDRA SOC and PT
- Summary of TEAEs leading to INCB001158 dose reduction by MedDRA SOC and PT
- Summary of TEAEs leading to discontinuation of INCB001158 by MedDRA SOC and PT
- Summary of TEAEs leading to discontinuation of pembrolizumab by MedDRA SOC and PT
- Summary of immune-related TEAEs by SOC and PT

8.3. Clinical Laboratory Tests

8.3.1. Laboratory Value Definitions

Laboratory values and change from baseline values will be summarized descriptively by visit. The baseline value will be determined using the nonmissing values collected before the first dose using the priority defined in Table 5. The last record before administration in the highest priority will be considered the baseline record. For baseline laboratory candidates with the same date and time in the same priority category, additional rules may be provided after consultation with the medical monitor to delineate which value will be defined as baseline.

Priority	Laboratory Visit	Central or Local Laboratory
1	Scheduled	Central
2	Scheduled	Local
3	Unscheduled	Central
4	Unscheduled	Local

Table 5:Identification of Baseline Record

Laboratory test values will be assessed for severity based on the numerical component of CTCAE v4.03.

8.3.2. Laboratory Value Summaries

All test results and associated normal ranges from central laboratories will be reported in SI units. Any laboratory test results and associated normal ranges from local laboratories will be converted to SI units.

When there are multiple nonmissing laboratory values for a participant's particular test within a visit window, the convention described in Table 6 will be used to determine the record used for by-visit tabulations and summaries. If a tie still exists, the laboratory value with the smallest laboratory sequence number will be used.

Priority	Laboratory Visit	Central or Local Laboratory	Proximity to Visit Window	Tiebreaker
1	Scheduled	Central	In-window	Use smallest
2	Scheduled	Local	In-window	laboratory sequence number
3	Unscheduled	Central	In-window	
4	Unscheduled	Local	In-window	
5	Scheduled	Central	Out-of-window	
6	Scheduled	Local	Out-of-window	

Table 6:	Identification	of Records f	for Postbaseline	Bv-Visit Summaries
	Inclusion	or records r	or i oscomsenne	

For coagulation and urinalysis laboratory values, listings will be provided.

Numeric chemistry and hematology laboratory values will be summarized descriptively in SI units, and non-numeric test values will be tabulated when necessary.

Severity grades will be assigned to laboratory test values based on the numerical component of CTCAE v4.03. The number of participants who experienced worsening of laboratory abnormalities will be summarized by maximum severity.

In cases where differentials of hematology parameters are obtained without corresponding absolute count data, efforts will be made to investigate if the conversion to an absolute value will lead to additional abnormalities. This will be discussed with the clinical team regarding appropriate documentation and action.

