has been updated in the protocol. Given the variability of urinary OA following a meal in healthy UCD carriers, separate thresholds have been defined for fasting patients (i.e., patients tested predose) versus those that have eaten (i.e., patients tested 6 hr postdose). In addition, since urinary OA elevations may be variable and have not been associated with evidence of clinically significant urea cycle inhibition, re-testing of urinary OA while the patient continues to receive INCB001158 is recommended in patients that have no evidence of clinically significant urea cycle inhibition (i.e., asymptomatic, plasma ammonia/BUN without significant change from baseline) in order to confirm that the elevation was not spurious. For elevations of urinary OA of  $> 15 \mu\text{mol}/\text{mmol}$  creatinine ( $>10\text{X}$  ULN) in fasting patients, dose reduction is recommended. This value is within the range of urinary OA elevations that were seen in the cohort of 24 healthy UCD carriers tested while fasting in Nagasaka *et al* (2013). For patients that are not fasting, higher elevations can be expected, based on the elevations in UCD carriers following a meal. Therefore, for elevations of urinary OA of  $> 60 \mu\text{mol}/\text{mmol}$  creatinine ( $40\text{X}$  ULN) at any time, dose reduction is recommended.

In summary, there has been no evidence of clinically significant inhibition of the urea cycle to date. Two patients have had asymptomatic transient elevations in urinary OA, a sensitive biomarker of hepatic urea cycle inhibition, that were not associated with changes in plasma ammonia or BUN, but were dose reduced based on the original protocol defined urinary OA threshold of  $5\text{X}$  ULN. Based on this clinical experience and a more extensive evaluation of the published data in healthy carriers of UCD genes, the approach to managing INCB001158 study drug in response to elevations in urinary OA has been changed in the current amendment. All of these data and the current management approach have been reviewed by an external clinical expert in the management of patients with UCD [REDACTED].

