### 12.1.3.3 Supportive Care Guidelines

Patients should receive appropriate supportive care measures as deemed necessary by the treating Investigator. Guidelines outlined below should be used in conjunction with information provided in the pembrolizumab product label:

**Hyperammonemia:** Patients should be monitored for elevated venous plasma ammonia. Asymptomatic clinically significant drug-related elevations in ammonia (e.g., a repeatable elevation in ammonia > 2x ULN AND > 2x baseline) should be managed by interrupting INCB001158 study drug and monitoring to resolution. For symptomatic elevations (i.e., significant ammonia elevation associated with nausea, vomiting, severe anorexia, mental status changes, seizure, or other symptoms associated with hyperammonemia), patients should be admitted for management according to the local institutional protocol for hyperammonemia, including 1) sending appropriate labs [ammonia (on ice, measured STAT), plasma amino acid profile, LFTs, electrolytes, bicarb, BUN, creatinine, glucose, and urine orotic acid], 2) IV hydration with dextrose-containing fluids, 3) discontinuation of protein intake, 4) implementing therapy to reduce ammonia levels (oral lactulose/lacitol, IV Ammonul), and 5) identifying and treating any potential triggers (e.g., discontinue corticosteroids, treat infections, etc).

**Diarrhea:** Patients should be monitored for signs and symptoms of enterocolitis (such as diarrhea, abdominal pain, blood or mucus in stool, with or without fever) and of bowel perforation (such as peritoneal signs and ileus). In symptomatic patients, infectious etiologies should be ruled out, and if symptoms are persistent and/or severe, endoscopic evaluation should be considered. In patients with severe enterocolitis, treatment with systemic corticosteroids should be initiated at a dose of 1 to 2 mg/kg/day of prednisone or equivalent. In patients that do not respond to high dose steroids with 72 hr, consider initiation of additional immunosuppressive therapy (e.g., infliximab). When symptoms improve to Grade 1 or less, corticosteroid taper should be started and continued over at least 1 month.

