**ATTACHMENT 2B: PHARMACOKINETIC [REDACTED] SAMPLING SCHEDULE FOR PARTS 2A, 2B, AND 2C**

Detailed instructions on sample collection and shipment can be found in the Laboratory manual.

Study Day (C=cycle, D=Day)	SPARSE SAMPLING PK GROUP: Patients in Parts 2a, 2b, and 2c					
	Time point 	PK [REDACTED]	Amino Acid Panel 	[REDACTED]	Urine sample for Orotic Acid 	Plasma Ammonia 
Screening						
C1, D1	Predose	3 mL	2 mL		2 mL	X
C1, D1	Postdose	3 mL 	2 mL 		2 mL 	X 
C1, D8	Predose				2 mL	X
C1, D15	Predose	3 mL	2 mL		2 mL	X
C1, D15	Postdose	3 mL 	2 mL 		2 mL 	X 
C1, D22	Predose				2 mL	X
C2, D1	Predose	3 mL	2 mL		2 mL	X
C3, D1	Predose	3 mL	2 mL		2 mL	X
C4, D1	Predose	3 mL	2 mL		2mL	X
Total sample collected		21 mL blood	14 mL blood			

- Where applicable, the collection window is ±15 minutes. Post dose time points for urine orotic acid collection window are ± 1 hour. The actual sample collection time will be entered in the EDC.

[REDACTED]

- The sample collection time points may be modified if the data indicate that these samples are no longer necessary to ensure patient safety. Pre-dose orotic acid will be collected any time prior to patient’s dosing. Where applicable, the post dose collection window is ± 1hr.

- Plasma ammonia samples will be collected and sent to the sites local laboratory.

[REDACTED]

- The PK postdose sample will be collected 1-4 hours post dose.
- The Orotic acid, amino acid, and ammonia samples will be collected 4-6 hours post dose.
- 2 mL blood will be collected in to one sodium heparin tube and processed for amino acid
- In addition to Orotic acid and plasma ammonia samples collected through Cycle 4 Day 1 (C4D1), samples will also be collected on Day 1 of every cycle (example, C5D1, C6D1, etc).

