**Serum Chemistry-Full Metabolic Panel (Peripheral Blood Sample) with additional analytes**

- |                        |   |
|------------------------|---|
| • Sodium               | • Uric acid                                   |
| • Potassium            | • Total protein                               |
| • Chloride             | • Albumin                                     |
| • CO 2      | • Total and direct bilirubin      |
| • Magnesium            | • Aspartate aminotransferase (AST)            |
| • Calcium              | • Alanine aminotransferase (ALT)              |
| • Phosphorus           | • Alkaline phosphatase (AP)                   |
| • Glucose  | • Lactate dehydrogenase (LDH)                 |
| • Blood urea nitrogen  | • Creatinine                                  |
| • Amino acid analysis  | • Thyroid Function Tests (TFTs)   |
| • Ammonia (venous)     | • Carcinoembryonic antigen (CEA)  |

 Fasting glucose (8-10 hour fast) is required on PK days only

 Direct bilirubin is only required if Total Bilirubin is above the upper limit of normal.

 Thyroid functioning will be monitored by measuring thyroid stimulating hormone (TSH) only, with a full panel run if there is an abnormal TSH result or if thyroid dysfunction is suspected

 Only in CRC patients

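### SAP Table 6 has no time-point field, so the by-visit chemistry summaries cannot show both predose and post-dose ammonia from the same visit

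*SAP*

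**What the plan says.** SAP 8.3.1 sets the frame: "Laboratory values and change from baseline values will be summarized descriptively by visit". Baseline is chosen separately, through Table 5: "The last record before administration in the highest priority will be considered the baseline record".

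SAP 8.3.2 and Table 6 then select postbaseline records for the by-visit summaries. The rule applies in this situation: "When there are multiple nonmissing laboratory values for a participant's particular test within a visit window". Table 6 ranks records by three attributes: scheduled or unscheduled, central or local laboratory, and in or out of window. Records that still tie are settled by sequence number: "If a tie still exists, the laboratory value with the smallest laboratory sequence number will be used". Time relative to dosing is not an attribute, and the SAP does not say how sequence numbers are assigned.

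The protocol plans more than one ammonia sample at some visits.

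- **Part 1a (Attachment 2A):** predose, 2 h and 6 h at C1D1, C1D15 and C2D8.
- **Parts 2a-2c, 1b and 3 (Attachments 2B and 2C):** predose and one post-dose sample at C1D1 and C1D15. A footnote in both attachments times the latter: "The Orotic acid, amino acid, and ammonia samples will be collected 4-6 hours post dose".

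Footnotes in all three attachments send ammonia to the site's local laboratory. Attachment 3 lists venous ammonia in the serum chemistry panel. SAP Appendix A plans chemistry summary tables for Parts 1a and 2 (3.3.1.2.1) and for Parts 1b and 3 (3.3.1.2.2), but none for Part 1c. It also plans a listing of orotic acid, BUN/urea and ammonia (numbered 2.85).

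**The concern.** Urea cycle inhibition is the on-target toxicity that the protocol singles out. Section 12.1.1 treats ammonia as the route to acute harm, and Section 5.1.2 makes symptomatic hyperammonemia a dose-limiting event. Post-dose samples were scheduled in addition to predose ones, yet the selection rule cannot tell them apart.

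By-visit displays also carry conclusions in this programme. Protocol Section 10.1.12 supports its statement that ammonia showed no dose-related trend with a by-visit-day table (Table 10.1-3). If the study report does the same from tables built under Table 6, a reader could take a statement about ammonia over time to cover post-dose values that the table does not contain.

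**Working it through.** There is no planned figure to reproduce. The check counts scheduled ammonia samples in Attachments 2A to 2C and applies Table 6 to them.

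**Step 1: do the samples tie?** At one visit the predose and post-dose samples are all scheduled and all local. If the visit is in window they share priority 2; if it is out of window they share priority 6. Either way, if same-day time points share one visit window (the literal reading), only the sequence number separates them.

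**Step 2: visits after C1D1 with post-dose ammonia.** Samples = visits × time points per visit. Records kept = one per visit.

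| Part | Visits | Samples | Records kept | Post-dose samples | Post-dose kept, numbering by time | Most post-dose kept under any numbering |
|---|---|---|---|---|---|---|
| 1a | C1D15, C2D8 | 2 × 3 = 6 | 2 | 2 × 2 = 4 | 0 | 2 |
| 2a-2c | C1D15 | 1 × 2 = 2 | 1 | 1 | 0 | 1 |
| 1b and 3 | C1D15 | 1 × 2 = 2 | 1 | 1 | 0 | 1 |

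With numbering by collection time, the loss is 4 of 4 post-dose values in Part 1a and 1 of 1 in the other parts. Where a post-dose value is kept instead, the predose value at that visit is lost. No numbering keeps both.

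**Step 3: C1D1.** The predose value here is the baseline record, and Table 6 is titled for postbaseline summaries. If the predose value is set aside as baseline, the first post-dose sample has the smallest remaining number and is kept.

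**Step 4: all scheduled samples through C4D1.**

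| Part | Samples | Post-dose | Post-dose kept, by time, C1D1 predose set aside | Post-dose kept, by time, C1D1 predose competing | Most post-dose kept under any numbering |
|---|---|---|---|---|---|
| 1a | 15 | 6 | 1 | 0 | 3 |
| 2a-2c | 9 | 2 | 1 | 0 | 2 |
| 1b and 3 | 8 | 2 | 1 | 0 | 2 |

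In Part 1a the value that may be kept at C1D1 is the 2 h sample after a single dose (Protocol 11.2.1.1). It says nothing about steady state.

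**Step 5: selection within visit and nominal time point.** The ties disappear, and all 6, 2 and 2 scheduled post-dose values enter the summaries.

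**The case against.** **Ammonia may not be in the chemistry tables.** Protocol Sections 11.2.1 and 11.2.2 name it beside serum chemistry, Attachments 1A and 1B give it its own row, and the SAP gives it its own listing. This is a fair reading, but it does not help the plan. Attachment 3 puts ammonia in the chemistry panel. If the SAP meant otherwise, ammonia would have only a listing and its post-dose values would still not be summarized.

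**Nothing is lost at patient level.** This stands. The urea-cycle listing is outside Table 6 and keeps every value. Table 6 does not restrict the worsening summary by maximum severity, although that summary uses numerical CTCAE grades and neither document shows one for ammonia. An elevation that changes study treatment is an adverse event under Protocol 16.1.1 and reaches the adverse event tables. Dose-limiting events are judged under the protocol, not from these tables. A reader might infer that the rule endangers patients or hides data; the documents do not support that.

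**The outcome depends on details not given.** This also stands. That the predose sample has the smallest number is an assumption, and so is the reading that same-day time points share a visit window. Sample displays are in a separate document. These gaps leave open which value is kept; they do not give Table 6 a time point.

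**Fasting and fed states.** A reader might go further and say that the tables would omit exactly the fed values for which the protocol sets a separate ammonia limit. It sets none. Its statement that "separate thresholds have been defined for fasting patients (i.e., patients tested predose) versus those that have eaten" concerns urinary orotic acid, and the ammonia criteria make no such distinction. Nor does post-dose always mean fed: in Part 1a, breakfast is first allowed 2 h after dosing on C1D1 and C1D15.

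**Conclusion.** The point holds as a gap in the rule for summarizing ammonia. Table 6 as written cannot carry predose and post-dose ammonia from the same visit. If sequence numbers follow collection time and time points share a visit window, the by-visit summaries lose all post-dose ammonia at C1D15 and C2D8: 4 of 4 samples per patient in Part 1a and 1 of 1 in Parts 2a-2c, 1b and 3. With other numbering, predose and post-dose values are mixed and the change from baseline is hard to interpret.

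It would go too far to say that no post-dose value can reach the summaries, because the first C1D1 value may survive. Part 1c is outside the point: it has no by-visit chemistry table for Table 6 to affect. The Part 2d sampling schedule is redacted and was not assessed.

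This should be corrected in the SAP, because it concerns a named on-target risk under the primary safety endpoint and the change is small.

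**What to change.** In SAP 8.3.2:

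1. Apply Table 6 within visit and nominal time point (predose, 2 h, 6 h, or 4-6 h) for any test with more than one planned sample per visit, and define how the sequence number is assigned.
2. State that ammonia is summarized by visit and time point, and name the tables.
3. Add each patient's maximum on-treatment ammonia.
4. Report by dose level the number (%) meeting the protocol's existing ammonia criterion as written: 2 times ULN and 2 times baseline, on repeated measurements or with symptoms (Protocol Table 12.1-1). A count of single values would drop the repeat-or-symptom condition. Section 12.1.3.3 words the asymptomatic case as "a repeatable elevation in ammonia > 2x ULN AND > 2x baseline", while Table 12.1-1 shows no greater-than sign. The two passages should be reconciled, and the SAP should cite the wording that it programs.

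SAP 8.5 already plans outlier counts for QT and QTcF, so a count of this kind fits the plan. The cost is SAP wording, a time-point variable in the laboratory programs and a few table shells. All data are already collected, and no clinical rule changes.

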## 15.5 Safety Analysis

Safety variables to be analyzed by dose level and tumor type are AEs, laboratory test results (hematology, coagulation, serum chemistry, and urinalysis), ECG, weight, and vital signs. Adverse event terms recorded on the eCRFs will be mapped to preferred terms using the most recent version of the Medical Dictionary for Drug Regulatory Activities (MedDRA®). All AEs will be summarized according to the system organ class and preferred term within the organ class. Adverse events will be tallied for overall frequency (number and percentage of patients), worst reported severity, and relationship to study treatment for each preferred term per patient. Serious adverse events will be similarly summarized. Listings of deaths, SAEs, and AEs leading to early termination of study treatment or premature withdrawal from study will also be provided.

Laboratory variables will be examined using mean change in value from baseline to scheduled time points. The baseline value of a variable is defined as the last value obtained on or before the date and time of the first dose of INCB001158 or pembrolizumab.

ECG, weight, and vital signs will also be summarized by changes from baseline to scheduled time points using descriptive statistics.

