8.5. Electrocardiograms

Twelve-lead ECGs including PR, RR, QT, QRS, and QTcF intervals will be obtained for each participant during the study. Baseline will be determined as the average of all nonmissing values before the first administration of INCB001158 or pembrolizumab. Listings will be provided for all ECG parameters.

Normal ranges for ECG values are defined in Table 8. Electrocardiogram values will also be considered abnormal if the absolute percentage change from baseline is more than 25% (30% for QRS interval). Participants exhibiting ECG abnormalities will be listed with study visit and assigned treatment group. Outliers of QT and QTcF values, defined as absolute values > 450 milliseconds, > 500 milliseconds, or change from baseline > 30 milliseconds, will be summarized.

		-5
Parameter	High Threshold	Low Threshold
PR	\leq 220 ms	≥ 75 ms
RR	≤ 1330 ms	$\geq 600 \text{ ms}$
QT	≤ 500 ms	\geq 300 ms
QRS	$\leq 120 \text{ ms}$	\geq 50 ms

 Table 8:
 Normal Ranges for Electrocardiogram Intervals

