9.1. Changes to Protocol-Defined Analyses

Not applicable.

QTcF

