4.1 Efficacy	
4.1.1	Kaplan-Meier Estimates of Progression-Free Survival
4.1.2	Kaplan-Meier Estimates of Duration of Response
4.1.3	Waterfall Plot of Best Percentage Change From Baseline in Sum of Target Lesions
4.1.4	Spider Plot of Sum of Target Lesions

Listings

Listing No.	Title
2.1.1	Participant Enrollment and Disposition Status
2.1.2	Participant Inclusion and Exclusion Criteria Violations
2.2	Protocol Deviations
2.3	Analysis Population
2.4.1	Demographic and Baseline Characteristics
2.4.2	Disease History
2.4.3	Prior Radiation Treatment
2.4.4	Prior Systemic Therapy
2.4.5	Prior Surgery or Surgical Procedure
2.4.6	Medical History
2.4.7	Prior and Concomitant Medication
2.4.8	Concomitant Procedures
2.5.1	Study Drug Compliance
2.5.2	Study Drug Administration
2.6.2	Best Overall Response, Duration of Response, and Progression-Free Survival
2.6.3	Response Assessment (Investigator Assessments)
2.6.4	Summary (Target Lesions)
2.6.5	Summary (Non-Target Lesions)
2.6.6	Summary (New Lesions)
2.6.7	ECOG Status
2.7.1	Adverse Events
2.7.2	Dose-Limiting Toxicities
2.7.3	Serious Adverse Events
2.7.4	Grade 3 and Higher Adverse Events
2.7.5	Adverse Events Leading to Interruption, Reduction, or Discontinuation of INCB001158 or Pembrolizumab
2.8.1	Clinical Laboratory Values – Hematology
2.8.2	Clinical Laboratory Values – Chemistry
2.8.3	Clinical Laboratory Values – Coagulation
2.8.4	Clinical Laboratory Values – Urinalysis
2.85	Clinical Laboratory Values – Orotic Acid, BUN/UREA, and Ammonia for Potential Urea Cycle Inhibition
2.8.6	Abnormal Clinical Laboratory Values
2.9.1	Vital Signs
2.9.2	Abnormal Vital Sign Values
2.10.1	12-Lead ECG Values
2.10.2	Abnormal 12-Lead ECG Values

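### The SAP drops change-from-baseline summaries that Protocol 15.5 plans for coagulation, urinalysis, ECG intervals and weight, and SAP 9.1 does not declare it

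*SAP*

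**What the plan says.** **Protocol.** Section 15.5 sets out the safety variables to be analysed by dose level and tumor type. Besides adverse events these are "laboratory test results (hematology, coagulation, serum chemistry, and urinalysis), ECG, weight, and vital signs". The method for the laboratory part is explicit: "Laboratory variables will be examined using mean change in value from baseline to scheduled time points". For the rest, "ECG, weight, and vital signs will also be summarized by changes from baseline to scheduled time points using descriptive statistics". Section 3.0 of the protocol and Table 1 of the SAP both place changes in laboratory values and vital signs in the primary endpoint for every part of the study.

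**SAP.**
- Section 8.3.1 starts broadly: laboratory values and their changes are to be described at each visit, and no panel is excluded.
- Section 8.3.2 narrows this: "Numeric chemistry and hematology laboratory values will be summarized descriptively in SI units", but "For coagulation and urinalysis laboratory values, listings will be provided".
- Section 8.4 promises values, change and percentage change for vital signs, naming systolic and diastolic pressure as included.
- Section 8.5 says "Listings will be provided for all ECG parameters" and adds a summary of QT and QTcF outliers, one category of which is a change of more than 30 ms.
- Weight appears in section 6.1.1 as a baseline characteristic.
- Section 9.1, on changes to protocol-defined analyses, reads "Not applicable".

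Urinary orotic acid appears in Appendix A only as part of a laboratory listing titled "Orotic Acid, BUN/UREA, and Ammonia for Potential Urea Cycle Inhibition".

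**The concern.** This trial has no primary efficacy endpoint (SAP 7.1), so its primary result is the safety description. When the protocol names a set of safety variables and a way to summarize them, and the SAP produces a shorter set while stating that nothing changed, a reader of the final report cannot tell that planned primary summaries are missing, or why.

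The practical loss is at group level. A listing shows each participant's values. It does not show whether mean INR, QRS duration or weight moved with dose or over time. Drifts that stay below an abnormality threshold in most individuals are what a change-from-baseline table is meant to reveal.

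**Working it through.** No sample size, power or error figure is involved, so the check sets the two documents side by side.

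| Variable | Protocol 15.5 | SAP text | SAP Appendix A | Match |
|---|---|---|---|---|
| Hematology | mean change | summary (8.3.2) | Tables 3.3.1.1.1, 3.3.1.1.2 | yes |
| Serum chemistry | mean change | summary (8.3.2) | Tables 3.3.1.2.1, 3.3.1.2.2 | yes |
| Coagulation | mean change | listing (8.3.2) | Listing 2.8.3 | no |
| Urinalysis | mean change | listing (8.3.2) | Listing 2.8.4 | no, for numeric parameters |
| ECG | descriptive change | listings, QT/QTcF outliers (8.5) | Tables 3.5.1.1, 3.5.1.2; Listings 2.10.1, 2.10.2 | in part |
| Weight | descriptive change | baseline only (6.1.1) | no post-baseline output named | no |
| Vital signs | descriptive change | value, change, % change (8.4) | tables for systolic and diastolic pressure; Listings 2.9.1, 2.9.2 | text yes, tables in part |

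**Counts.**
- Laboratory groups with a summary table: 2 of 4.
- ECG intervals in section 8.5 (PR, RR, QT, QRS, QTcF) with a descriptive change table: 0 of 5. Two of the five, QT and QTcF, get outlier counts. Percentage changes above 25% (30% for QRS) are flagged as abnormal, but those participants are listed, not counted.
- Vital signs in SAP Table 7 (systolic, diastolic, pulse, temperature, respiratory rate) with a table: 2 of 5.
- Weight: no post-baseline output. It is not among the Table 7 parameters, so section 8.4 does not clearly bring it in.

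**Are the data there?** Yes. Protocol Attachments 1A and 1B schedule coagulation tests and weight at most treatment visits, urinalysis on Day 1 of each cycle, and ECGs at screening, Cycle 1 Days 1 and 15, and end of treatment.

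**Internal consistency.** Section 8.3.1 covers all laboratory values and section 8.3.2 removes two groups. The two sections cannot both be followed for coagulation and numeric urinalysis.

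**Orotic acid, checked separately.** Protocol 15.5 does not name it, and section 11.2.1 lists the urine sample for it apart from the clinical laboratory evaluation. Attachment 3 includes ammonia and blood urea nitrogen in the serum chemistry panel but not orotic acid. The chemistry tables should therefore carry ammonia and BUN by visit, but not orotic acid. Section 5.1.2 makes its elevation a dose-limiting event. Section 10.1.12 reports elevations in 2 of 3 patients at 150 mg BID and no significant changes at 50 or 100 mg BID.

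**The case against.** **All analyses are exploratory and the SAP allows listings.** SAP 3.2 calls every analysis exploratory, and 8.1 lets listings replace tables when appropriate. But the example in 8.1 is a sparse adverse event table, which does not fit coagulation or weight, measured repeatedly in nearly everyone. Exploratory status lowers the stakes; it does not make section 9.1 accurate.

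**Appendix A is only a guideline.** This stands for vital signs: the text of 8.4 is general, so a reader who infers that only blood pressure will be analysed goes too far. It does not rescue coagulation, urinalysis or ECG, where the body text itself specifies listings.

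**ECG change is not ignored.** This stands. QT and QTcF changes above 30 ms are counted in two planned tables. A reader might infer that ECG results are listed only; that is wrong. What is missing is descriptive change.

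**Orotic acid.** A reader might infer that the SAP breaks a protocol promise to summarize it, or that the report will hold nothing on threshold crossings by dose. The documents support neither.
- Section 15.5 does not mention orotic acid, and 10.1.12 calls it a biomarker, not a toxicity.
- SAP section 1 defers pharmacodynamic methods to a separate document, so a summary may exist there.
- Under Protocol 16.1.1 an abnormality that requires a change in study treatment is an adverse event, and Table 12.1-1 calls for interruption above its thresholds. Such crossings should reach the treatment-emergent event tables, and SAP 8.2.2 lists DLTs by dose level.
- The 150 mg elevations were asymptomatic, came from three patients, and were acted on under a superseded threshold of 5 × ULN.

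These outputs still do not give crossing rates with a denominator of participants tested. Presentation by dose level is optional in SAP 5.1, and the interruption count in 8.2.3 is not broken down by event term.

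**Conclusion.** The discrepancy is real and undeclared. Coagulation and numeric urinalysis lose the mean-change summary in Protocol 15.5, the five ECG intervals lose the descriptive change summary, and weight loses any post-baseline analysis. The entry in SAP 9.1 is therefore incorrect. Coagulation and urinalysis fall within the laboratory part of the primary endpoint. ECG and weight are not named in that endpoint but are named in section 15.5. For the remaining vital signs the defect is only that Appendix A lags behind section 8.4.

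The consequence is incomplete group-level safety reporting. No type I error, power or sample size changes, and coagulation, urinalysis and ECG values remain available in listings. The conclusion assumes that no other document restores these summaries; the SAP mentions a separate document only for pharmacokinetic and pharmacodynamic methods.

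The orotic acid table is a recommendation, not a correction of a broken commitment, and it lapses if the separate pharmacodynamic plan already provides one.

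**What to change.** 1. Add change-from-baseline tables to SAP 8.3.2, 8.5 and Appendix A for coagulation, numeric urinalysis parameters, the ECG intervals (PR, RR, QRS, QT, QTcF) and weight, at scheduled visits and by treatment group and dose level.
2. Extend the Appendix A vital sign tables to pulse, temperature and respiratory rate, to match section 8.4.
3. Reword 8.3.1 and 8.3.2 so that they agree.
4. If any of these summaries is deliberately dropped, replace the entry in 9.1 with a statement of what was dropped and why.

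Separate improvement, unless covered elsewhere: tabulate fasting orotic acid by visit and dose level, with numbers and denominators of participants crossing the protocol's own urea-cycle thresholds. Protocol Table 10.1-5 already shows predose values by visit. Sections 5.1.2 and Table 12.1-1 must be reconciled first, since one sets the fasting criterion at ≥ 10 × ULN and the other at > 10 × ULN. For ammonia and BUN only the crossing counts would be new.

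The cost is a few extra tables from data already collected and a corrected section 9.1.
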